6.2.1.2.2 Grading of Troponin-I Elevation

Central testing of cardiac troponin-I will be performed for eligibility determination, grading, and withholding decisions. The following criteria is developed based on CTCAE 5.0 to determine the grade of troponin-I elevation with ADVIA Centaur XP TnI assay performed by central lab:

- grade 1: isolated elevation of troponin > 99th percentile Upper Reference Limit (URL) of 0.04 ng/mL for females and 0.059 ng/mL for males
- grade 3: troponin elevation greater than or equal to manufacturer's defined cut-off for MI of 0.78 ng/mL

Dose Cohort Stopping Rules

The DLRT will recommend stopping or modifying dosing if suspected adverse drug reactions, changes in vital signs, ECG, or clinical laboratory results are observed and these changes pose a significant health risk. The Amgen Medical Monitor may suspend dosing and convene a DLRM at any time based on emerging safety data.

Clinically or medically significant suspected adverse drug reactions, and serious adverse events considered to be related to study procedures will be followed until resolved or considered stable.

The study may be terminated at any point at the discretion of the sponsor.

6.2.2 Dosage Adjustments, Delays, Rules for Withholding or Restarting, Permanent Discontinuation

For Hematologic Drug-Related Adverse Events (AE)

Dose reduction/interruption/discontinuation decisions should be based on the National Cancer Institute (NCI) CTCAE version 5.0 of the toxicity and the guidelines provided below. Dose modifications outside of those provided in Table 6-3 are allowable after discussion with the PI and documentation in the medical record, if in the best interest of the patient.

Patients with HR- MDS usually present with abnormal peripheral blood counts at the time therapy is started, and myelosuppression is an expected event during the course of therapy. Thus, no dose adjustments or treatment interruptions for myelosuppression will be planned in the presence of residual MDS. Dose-interruptions of azacitidine and AMG 176 in these patients should be considered on an individual case and discussed with the PI.

Protocol Number: 20200392

Date: 28 April 2022 Page 63 of 149

Patients with a response (with decline in blasts < 5%) who have prolonged (> 28 days) count recovery, may have the treatment with azacitidine and AMG 176 interrupted at the discretion of the treating physician after discussing with the PI until neutrophils recover to Absolute Neutrophil Count (ANC) is $\geq 500/\mu L$ and PLT to > $50 \times 10^9/L$. Investigators should, whenever possible, determine which medication is causing the toxicity and interrupt or dose reduce azacitidine and/or AMG 176, as applicable. After interruption, dose adjustment for azacitidine, AMG 176, or both can be made as follows:

- A reduction of two dose levels or holding of AMG 176 on day 22 may be considered
 if the myelosuppression or was deemed severe and life threatening by the treating
 physician, and if it is in the patient's best interest.
- If additional dose reductions are thought to be necessary by the investigator, a discussion with the PI or co-PI is required on an individual case.

For Non-Hematologic Drug-Related AEs

Investigators should, whenever possible, determine which medication is causing the toxicity and interrupt or dose reduce azacitidine and/or AMG 176, as applicable. Dose reductions will be as per Table 6-3 recommendations. Dose reductions different than Table 6-3 are allowed if determined to be in the patient's best interest and rationale documented in patient record. The investigators will use their clinical judgment to determine whether toxicity is caused by azacitidine, AMG 176, or both. Dose reductions of one of the agents, or both, are allowed after discussion with the PI or co-PI and documentation in the medical record.

Protocol Number: 20200392

Date: 28 April 2022 Page 64 of 149

Table 6-3. Dose Adjustments for Non-hematologic AEs That Are at Least Possibly Related

| Grade | Occurrence | Dose Modification | | |
|--|-----------------------|---|--|--|
| 1 or 2 | Anytime | No dose reduction | | |
| 3 or 4 Persistent grade 2: consider similar dose adjustments if persistent and not responding to optimal management in the opinion of PI and treating physician | First and second time | Hold AMG 176 ± azacitidine. Resume AMG 176 ± azacitidine a prior dose if recovery to ≤ grade 1 occurs within 14 days. If toxicity persists for 15 to 28 days, hold therapy and resume azacitidine and AMG 176 at prior dose if recovery to ≤ grade 1 or resume AMG 176 ± azacitidine at ONE dose level below current dose if recovery to ≤ grade 2. | | |
| | Third and fourth time | Hold AMG 176 ± azacitidine. Follow until toxicity ≤ grade 2. Resume AMG 176 ± azacitidine at ONE dose level below current dose. | | |
| | Fifth time | Hold AMG 176 ± azacitidine. Follow until toxicity ≤ grade 2. Resume AMG 176 ± azacitidine at TWO dose levels below current dose. | | |

PI = Principal Investigator.

Other Modifications of Dose Schedules

- Further dose reductions can be made to prevent adverse events and keep clinically significant toxicities grade ≤ 2.
- Dose adjustments by more than one dose level at a time can be considered when judged in the best interest of the patient (eg, severe myelosuppression) when toxicity has resolved. The reason for this reduction will be discussed with the PI or co-PI and documented in the medical record.
- Treatment interruptions and dose modifications other than the ones mentioned above
 can be considered after discussion with the PI and proper documentation of the
 rationale. Dose adjustment/delay of only one of the agents is permissible if the toxicity
 is most likely judged to be related to one of the agents by the investigator.

Supportive Care

Supportive care measures including blood products, infection prophylaxis, and growth factors will be administered according to institutional and Leukemia Department guidelines.

6.2.2.1 Amgen Investigational Product: AMG 176

The reason for dose change of AMG 176 is to be recorded on each subject's CRF(s).

Protocol Number: 20200392

Date: 28 April 2022 Page 65 of 149

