^p Cytomorphology: bone marrow smears (slides) at screening, pre-dose on day 1 of cycle 2 and cycle 3 and thereafter prior to every other cycle or when clinically indicated until disease progression. Bone marrow biopsies/aspirates may be performed with a ± 3 day window.

- ^q EOT and SFU: In any case of premature treatment discontinuation, the investigator should make every effort to perform all examinations scheduled for the EOT and SFU visits. These data should be recorded, as they comprise an essential evaluation that should be performed prior to removing any subject from treatment and to allow for the evaluation of the study endpoints. The EOT visit will occur upon the decision to end the treatment (eg, due to intolerable AE, disease progression). The SFU visit will occur 30 days (+ 3 days) after last dose of protocol required therapies.
- Note: If a subject withdraws consent, it is important to distinguish between withdrawal of consent from treatment (partial withdrawal of consent) which will allow for continued follow-up in LTFU (eg, for survival) or withdrawal of consent from study (full consent withdrawal). These discussions should be thoroughly documented in the subject's medical records.
- LTFU/EOS: Long-term follow-up (LTFU) visits will occur every 3 months for up to 1 year after EOT. The EOS for a subject will occur when the subject completes the LTFU or dies, whichever occurs first.
- Note: If a subject withdraws consent, it is important to distinguish between withdrawal of consent from treatment which will allow for continued follow-up in LTFU (eg, for survival) or withdrawal of consent from study. These discussions should be thoroughly documented in the subject's medical records.
- ^s During the Long-term follow-up phase, serious adverse event(s) suspected to be related to Investigational Product will be reported to Amgen. After end of study serious adverse event(s) suspected to be related to Investigational Product will be reported to Amgen. Please refer to Section 8.4.6.1.3 for additional details.

Protocol Number: 20200392

Date: 28 April 2022 Page 28 of 149

2. Introduction

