6.2.2.3 Amgen/Non-Amgen Non-Investigational Product: Azacitidine

The reason for dose change of azacitidine is to be recorded on each subject's CRF(s). For contraindications, warnings, precautions, and potential drug interactions please refer to the current prescribing information for azacitidine.

Azacitidine dose adjustments based on hematology laboratory values:

Hematological toxicity is defined as the lowest count reached in a given cycle (nadir) if platelets ≤ 50.0 x 10⁹/L and/or ANC ≤ 1 x 10⁹/L.

Recovery is defined as an increase of cell line(s) where hematological toxicity was observed of at least half of the difference of nadir and the baseline count plus the nadir count (ie, blood count at recovery \geq to nadir count + (0.5 x [baseline count - nadir count]).

• Subjects without reduced baseline blood counts (ie, White Blood Cells [WBC] $\geq 3.0 \times 10^9$ /L and ANC $\geq 1.5 \times 10^9$ /L, and platelets $\geq 75.0 \times 10^9$ /L) prior to the first treatment.

For subjects with baseline (start of treatment) WBC \geq 3.0 x 10⁹/L, ANC \geq 1.5 x 10⁹/L, and PLT \geq 75.0 x 10⁹/L, adjust the dose as follows, based on nadir counts for any given cycle (see Table 6-4):

Table 6-4. Azacitidine Hematology Dose Reduction Guidance

| Nadir counts | | |
|----------------------------|----------------------------------|--------------------------|
| ANC (x 10 ⁹ /L) | Platelets (x 10 ⁹ /L) | % Dose in the Next Cycle |
| < 0.5 | < 25.0 | 50% |
| 0.5 to 1.5 | 25.0 to 50.0 | 67% |
| > 1.5 | > 50.0 | 100% |

ANC = absolute neutrophil count.

For patients whose baseline counts are WBC $< 3.0 \times 10^9$ /L, ANC $< 1.5 \times 10^9$ /L, or platelets $< 75.0 \times 10^9$ /L, dose adjustments should be based on nadir counts and bone marrow biopsy cellularity at the time of the nadir as noted below (see Table 6-5), unless there is clear improvement in differentiation (percentage of mature granulocytes is higher and ANC is higher than at onset of that course) at the time of the next cycle, in which case the dose of the current treatment should be continued.

Protocol Number: 20200392

Date: 28 April 2022 Page 70 of 149

Table 6-5. Azacitidine Dose Reduction Based on Bone Marrow Cellularity

| WBC or Platelet Nadir % — | Bone Marrow Biopsy Cellularity at Time of Nadir (%) | | | |
|----------------------------------|---|----------|------|--|
| decrease in counts from baseline | 30 to 60 | 15 to 30 | < 15 | |
| | % Dose in the Next Cycle | | | |

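### Protocol Sections 6.2.2 and 6.2.2.3 give incompatible azacitidine rules for myelosuppression while residual MDS is present, and no text says which one governs.

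*Protocol*

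**What the plan says.** **Section 6.2.2, hematologic events.** The text introduces the population with "Patients with HR- MDS usually present with abnormal peripheral blood counts at the time therapy is started", treats myelosuppression as expected, and concludes that "no dose adjustments or treatment interruptions for myelosuppression will be planned in the presence of residual MDS". The next sentence shows that both drugs are meant: "Dose-interruptions of azacitidine and AMG 176 in these patients should be considered on an individual case and discussed with the PI". Changes outside Table 6-3 are also permitted after discussion with the PI and documentation.

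**Section 6.2.2.3, azacitidine.** Under the lead-in "Azacitidine dose adjustments based on hematology laboratory values", subjects are split by baseline counts only.

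- Baseline counts not reduced: "adjust the dose as follows, based on nadir counts for any given cycle" (Table 6-4, giving 100%, 67% or 50% of the dose in the next cycle).
- Baseline WBC, ANC or platelets reduced: "dose adjustments should be based on nadir counts and bone marrow biopsy cellularity at the time of the nadir" (Table 6-5, giving 100%, 75%, 50% or 33%). The one exception is clear improvement in differentiation.
- After a nadir as defined in that table, the next course waits if counts are not more than 25% above the nadir by day 28. Counts are then rechecked weekly, and half the scheduled dose is given if there is no 25% rise by day 42.

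**Marrow schedule (Section 1.3, footnote p).** Marrow is taken at screening, then "pre-dose on day 1 of cycle 2 and cycle 3 and thereafter prior to every other cycle", or when clinically indicated.

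**The concern.** A site treating a subject with residual MDS after a low nadir finds two defaults. Section 6.2.2 plans no adjustment. Section 6.2.2.3 gives a percentage to apply to the next cycle and, for some subjects, a delay. Both halves of the Section 6.2.2 statement, adjustments and interruptions, are contradicted.

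This overlap is not a rare corner. Part 1 enrols relapsed or refractory MDS after HMA failure (Section 5.1), so subjects enter with active disease. Section 6.2.2 itself describes abnormal baseline counts as usual, and reduced baseline counts are what send a subject to Table 6-5.

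If investigators resolve the conflict differently, azacitidine dose intensity from cycle 2 depends on which page was read. That would affect observed myelosuppression and the data feeding the integrated assessment that selects the combination MSBED (Section 4.1.1). In the design as written, it would also affect the Part 2 response rate.

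**Working it through.** There is no power or error-rate figure to reproduce. The check compares the texts and then reads off the doses.

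**Step 1: do the two rules cover the same drug, trigger and subjects?**

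- Drug: Section 6.2.2 names azacitidine, and Section 6.2.2.3 is about azacitidine. Same.
- Trigger: myelosuppression in one, nadir ANC, WBC and platelets in the other. Same.
- Subjects: Section 6.2.2 is conditioned on residual MDS. Section 6.2.2.3 is conditioned on baseline counts, with no mention of residual disease. A subject with residual MDS therefore meets both.

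**Step 2: does any text rank them?** None was found. The differentiation exception in the Table 6-5 rule is a different condition from residual MDS. Being a subsection does not settle precedence either, because the parent text names azacitidine and says the opposite.

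**Step 3: size.** The starting dose is 75 mg/m² daily for 7 days (Section 4.3.2). Next-cycle daily dose = 75 × table percentage.

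| Rule | Condition | Fraction | Daily dose (mg/m²) |
|---|---|---|---|
| Section 6.2.2 | residual MDS, no planned change | 1.00 | 75 |
| Table 6-4 | middle row | 0.67 | 50.25 |
| Table 6-4 | lowest row (ANC < 0.5, platelets < 25.0 × 10⁹/L) | 0.50 | 37.5 |
| Table 6-5 | fall 50–75%, cellularity 30–60% | 1.00 | 75 |
| Table 6-5 | fall > 75%, cellularity 30–60% | 0.75 | 56.25 |
| Table 6-5 | either fall, cellularity 15–30% | 0.50 | 37.5 |
| Table 6-5 | either fall, cellularity < 15% | 0.33 | 24.75 |

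Extremes: 75 / 37.5 = 2.0 under Table 6-4 and 75 / 24.75 = 3.0 under Table 6-5. Over seven days this is 525 mg/m² against 262.5 or 173.25 mg/m². In one Table 6-5 cell the two sections agree on dose.

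**Step 4: timing.** The day 28 to day 42 rule can move the next course by up to 42 − 28 = 14 days before the half dose is given. Section 6.2.2 plans no interruption for the same finding.

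**Step 5: when and where it applies.** Section 4.3.2 fixes the first-cycle azacitidine dose regardless of baseline counts, and the tables act on the next cycle. The conflict therefore starts at cycle 2 and exists only where azacitidine is given, in Parts 1B and 2.

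**Step 6: two neighbouring ambiguities in Section 6.2.2.3.**

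- Hematological toxicity is defined with ANC at or below 1 × 10⁹/L and/or platelets at or below 50 × 10⁹/L, while the 67% row of Table 6-4 runs from ANC 0.5 to 1.5. A subject with ANC 1.2 and platelets 60 has no toxicity by the definition, sits in the 67% row on ANC and in the 100% row on platelets. How the definition bears on the rows is not said.
- Table 6-5 needs biopsy cellularity at the nadir. Footnote p sets no fixed nadir marrow but permits one when clinically indicated, and Section 8.3.1 permits additional marrow at the investigator's discretion.

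**The case against.** The best defence is that the two sections can live together. Section 6.2.2 does not mandate full dose: it permits individual-case interruption and other modifications after discussion with the PI. Table 6-4 is titled as guidance, and the Table 6-5 wording is advisory. On this view 6.2.2.3 is simply the specific rule for azacitidine. This does not resolve the point. Discretion to depart from a default does not say which default a site starts from, and the general text includes azacitidine by name.

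Other parts of the defence stand, and they limit what a reader should infer.

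- **That counts alone can bring the dose to 33%.** They cannot. That cell needs a fall of at least 50% and cellularity below 15%. On counts alone the lowest Table 6-4 entry is 50%.
- **That every affected subject faces a two- to three-fold difference.** Those are the extremes. Intermediate rows differ less, and one cell gives 100%.
- **That the nadir marrow cannot be obtained.** Footnote p and Section 8.3.1 allow it. It is unscheduled, not prohibited.
- **That the toxicity definition contradicts Table 6-4.** The definition feeds the definition of recovery that follows it, while Table 6-4 is keyed to nadir counts. This is unclear drafting, not a proven contradiction.
- **That dose escalation or reported efficacy is compromised.** The minimum DLT window is cycle 1 (Section 6.2.1.1), before any reduction applies, so cycle 1 DLT counts are largely untouched. The SAP marks Part 2 as not enrolled (Section 3.1), plans no analysis of the Part 1B response endpoints (Section 10), and lists azacitidine exposure as not applicable (Section 9.6.9). No planned efficacy analysis carries the effect.

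**Conclusion.** The protocol is internally contradictory on azacitidine dosing for myelosuppression in the presence of residual MDS. A site cannot follow both sections as written. For the same findings the next-cycle dose could be 75 mg/m² under Section 6.2.2 and, at the extremes, 37.5 mg/m² or about 25 mg/m² under Section 6.2.2.3, with a possible two-week delay.

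This rests on two readings: that a subject with residual MDS falls under Section 6.2.2 whatever the baseline counts, and that Section 6.2.2.3 applies to all azacitidine-treated subjects because it states no exception for residual disease. The dose comparison also assumes no case-by-case change agreed with the PI and a scheduled dose of 75 mg/m².

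The defect is confined to cycle 2 onward in the combination parts. With the study terminated early and Part 2 not enrolled, its practical effect is limited, but the governing text is still wrong as written. The ANC and marrow-timing points are matters for clarification in the same edit, not separate contradictions.

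**What to change.** Reconcile Sections 6.2.2 and 6.2.2.3 so that one stated rule governs azacitidine for myelosuppression in the presence of residual MDS. The rule should also cover the day 28 and day 42 provisions and be cross-referenced in both places. The sponsor decides which rule holds.

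In the same edit:

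- state how the hematological-toxicity definition relates to the ANC rows of Table 6-4;
- reconcile the nadir-timed cellularity in Table 6-5 with the marrow schedule in Section 1.3.

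No position is taken on which dose, threshold or marrow sample is right. For the contradiction itself the cost is amendment wording. Whether the marrow clarification adds any procedure depends on what the sponsor chooses.

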6.2.2.1.1 Dosage Adjustments

Upon completion of the lead-in dosing if applicable, the subject should continue on the same target dose of AMG 176 throughout the study unless the following events occur:

- For subjects experiencing an adverse event meeting the DLT definition or intolerable related adverse events BUT showing evidence of response, there will be an option to reduce the dose to the immediate next lower dose level shown to be safe and tolerable in the dose escalation part of the study.
- The study drug can be resumed once the adverse events recover to baseline or grade 1 and the reintroduction of AMG 176 is deemed safe by the Investigator and Amgen's Medical Monitor.
- Subjects must be informed of the risk of continuing on therapy. Each subject is only
 allowed a single dose reduction as a result of an adverse event. Subjects showing
 evidence of response or subjects who in the opinion of the investigator may be
 responding to AMG 176, may have the option to have more than single dose
 reduction if deemed safe by the Investigator and Amgen's medical monitor.
- For subjects who experience grade 3 arrhythmia possibly associated with AMG 176, AMG 176 dosing must be resumed at the immediate next lower dose level if the requirements mentioned below in rules for restarting are met.
- For subjects meeting the withholding criteria for elevation of cardiac troponin
 (> 0.1 to < 0.78 ng/mL), AMG 176 dosing can be resumed at the immediate next
 lower dose level if the requirements mentioned below in rules for dose withholding
 are met.

Subjects should not be re-challenged with AMG 176 if the following AMG 176-related adverse events occur:

- Any life-threatening adverse events
- Drug-Induced Liver Injury (DILI) meeting Hy's law (see Section 11.7)
- Persistent grade 3 adverse events that do not recover to baseline or grade 1 within 4 weeks.
- Any AMG 176 related adverse event meeting DLT-criteria that recurs despite 2 dose level reductions.

6.2.2.1.2 Dosage Delays

During the DLT evaluation period, if the dosing is delayed for more than 2 weeks the subject will be removed from the study and will be replaced. After DLT evaluation period, if the dosing is delayed for < 4 weeks, the subject should resume the treatment as soon as possible if deemed safe by the investigator. The investigator should inform the Amgen Clinical team as soon as the unexpected dosing interruption occurs. If the dosing of AMG 176 is delayed > 4 weeks (missing 1 cycle) due to AMG 176-related adverse events, the subject will be permanently removed from AMG 176 treatment. If the dosing delay occurred under conditions other than those associated with

Protocol Number: 20200392

Date: 28 April 2022 Page 66 of 149

AMG 176-related toxicities, the case will be reviewed by Amgen Medical Monitor to determine whether the subject will be allowed to resume AMG 176 treatment.

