6.2.1.1 Dose-limiting Toxicity Evaluation Period

The minimum DLT evaluation period is defined as 28-days of treatment in cycle 1.

The DLT evaluation period may also be extended to assess events starting within the evaluation period in case the DLT definition is time dependent (neutropenia or thrombocytopenia, see below).

Subjects are considered DLT-evaluable if they experienced a DLT during the DLT evaluation period or if they received 75% of the planned doses of AMG 176 (and 100% of the planned doses of azacitidine in Part 2) and completed the DLT evaluation period.

Subjects who do not complete 75% of the planned doses of AMG 176 (and 100% of the planned doses of azacitidine) or discontinue from the study prior to completing the DLT evaluation period for reasons other than a DLT will be considered non DLT-evaluable for dose escalation decisions and OBD/MSBED determination and will be replaced by an additional subject at that same dose level. Subjects who receive supportive care during the DLT evaluation period that confounds the evaluation of DLTs (not including supportive care described in Section 6.2.1.2 as part of the DLT definition) may be considered non evaluable for dose escalation decisions and MSBED determination and replaced at the discretion of the Medical Monitor.

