| Exceptions | Infections and most hematologic adverse events Non-hematologic adverse events: grade 3 weight gain or loss grade 3 diarrhea despite optimal anti-diarrheal therapy that resolves to ≤ grade 2 within < 72 hours with or without clinical intervention grade 3 or 4 isolated electrolyte abnormalities that is not clinically significant and resolves to ≤ grade 2 within 72 hours with or without clinical intervention grade 3 nausea and vomiting that does not require tube feeding, total parenteral nutrition, or prolonged hospitalization and resolves to ≤ grade 2 within < 72 hours with or without clinical intervention grade 3 or 4 serum lipase without clinical signs or symptoms of pancreatitis that returns to baseline within 72 hours of interrupting study drug infection grade 3 (with concurrent neutropenia grade 3 or 4) that resolves to ≤ grade 2 within 7 days with or without clinical intervention grade 3 fatigue or asthenia grade 3 constipation that resolves to ≤ grade 2 within 7 days with or without clinical intervention |

AE = adverse event; AML = acute myeloid leukemia; ALT = alanine aminotransferase; AST = aspartate aminotransferase; CMML = chronic myelomonocytic leukemia; DILI = drug-induced liver injury; DLT = dose limiting toxicity; ECG = electrocardiogram; LVEF = left ventricular ejection fraction; MDS = myelodysplastic syndrome; QTcF = QT interval with Fridericia's correction; TLS = tumor lysis syndrome; ULN = upper limit of normal.

^a Further treatment with AMG 176 may be considered for grade 1 elevations of troponin-I after a cardiology evaluation is completed and results are discussed with the Amgen Medical Monitor.

Protocol Number: 20200392

Date: 28 April 2022 Page 62 of 149

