6.2.2.2 AMG 176 Management of Toxicities

6.2.2.2.1 Management of Infections

Subjects with evidence of existing infection should be closely monitored while being treated with AMG 176. Subjects with active systemic infections requiring IV antibiotics, antivirals, or antifungals should not be dosed with AMG 176 until infection has resolved and if being treated with an anti-infectious therapy, the course of such therapy should have been completed. Management should be tailored to the appropriate prophylaxis and/or treatment for the underlying infection according to the local SOC and institutional guidelines with the exception of excluded medications detailed in Section 6.1.7.

Infection Prophylaxis

Subjects who may experience neutropenia are at a high risk for infectious complications. As appropriate, these subjects should be administered prophylactic antibacterial (eg, treatment with ciprofloxacin) and antifungal (treatment with amphotericin B or echinocandins).

Protocol Number: 20200392

Date: 28 April 2022 Page 68 of 149

These subjects should be monitored for early signs of breakthrough infections after the initiation of antibacterial therapy to prompt additional evaluation and possible therapy modification. Subjects experiencing diarrhea should be closely monitored for their electrolyte levels.

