7.1 Discontinuation of Study Treatment

Subjects (or a legally acceptable representative) can decline to continue receiving investigational product and/or other protocol-required therapies and/or procedures at any time during the study but continue participation in the study. If this occurs, the investigator is to discuss with the subject the appropriate processes for discontinuation from investigational product or other protocol-required therapies and must discuss with the subject the possibilities for continuation of the Schedule of Activities (see Table 1-1) including different options of follow-up (eg, in person, by phone/mail, through family/friends, in correspondence/communication with other treating physicians, from the review of medical records) and collection of data, including endpoints, adverse events, and must document this decision in the subject's medical records. Subjects who have discontinued investigational product and/or other protocol-required therapies and/or procedures should not be automatically removed from the study. Whenever safe and feasible, it is imperative that subjects remain on-study to ensure safety surveillance and/or collection of outcome data.

Reasons for early removal from protocol-required investigational product(s) or procedural assessments may include any of the following:

- Decision by Sponsor
- Lost to follow-up
- Death
- Adverse event
- Subject request
- Ineligibility determined
- Protocol deviation
- Non-compliance (eg, procedural or dosing as defined in Section 6.1.1)
- Disease progression according to the Uniform Response Criteria for MDS/MPN, and/or per institutional guidelines as applicable
- Requirement for alternative therapy
- Pregnancy

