7.2.1 Reasons for Removal From Study

Reasons for removal of a subject from the study are:

- Decision by sponsor
- Withdrawal of consent from study
- Death
- Lost to follow-up

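### A dosing delay of more than 2 weeks in the DLT evaluation period takes the subject off the study, not just off treatment; this conflicts with Protocol Section 7.1 and puts some long-term cardiac follow-up at risk (minor impact)

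*Protocol*

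**What the plan says.** Protocol Section 6.2.2.1.2 (Dosage Delays) sets two limits on delay and attaches different consequences to them.

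- **In the DLT evaluation period**, the rule reads: "if the dosing is delayed for more than 2 weeks the subject will be removed from the study and will be replaced". The sentence names no cause.
- **After that period:** for a delay of more than 4 weeks due to AMG 176-related events, "the subject will be permanently removed from AMG 176 treatment".

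The section closes by sending delays not associated with AMG 176 toxicity to the Medical Monitor, who decides on resumption. It does not say whether this also applies in the DLT evaluation period.

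Other sections bear on the first limit:

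- **Section 7.1:** "Subjects who have discontinued investigational product and/or other protocol-required therapies and/or procedures should not be automatically removed from the study". It calls for subjects to stay on study whenever that is safe and feasible, and offers phone, mail and record review as ways of following them.
- **Section 7.2.1** introduces its list with "Reasons for removal of a subject from the study are". The four entries are sponsor decision, withdrawal of consent, death and loss to follow-up. Dosing delay is not among them.
- **Section 6.2.1.1:** a subject who falls short on planned doses, or leaves before the period ends, for reasons other than a DLT is non-evaluable and "will be replaced by an additional subject at that same dose level".
- **Section 8.1.5:** LTFU runs every 3 months for 1 year after end of treatment (EOT). It covers survival, subsequent anti-cancer therapy, cardiac serious adverse events and cardiac diagnostics, with an echocardiogram at the first visit.

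**The concern.** A subject who meets the 2-week limit has stopped AMG 176, and the rule then ends study participation automatically. Section 7.1 tells the site not to do that. Section 6.2.2.1.2 itself separates leaving treatment from leaving the study, so it is hard to read one as meaning the other.

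A hold that the protocol itself requires can lead here without a DLT. Under Section 6.2.2.2.1, "Subjects with active systemic infections requiring IV antibiotics, antivirals, or antifungals should not be dosed with AMG 176 until infection has resolved", and the treatment course must also be complete. Table 6-2 lists "Infections and most hematologic adverse events" among the DLT exceptions, although a narrower line on grade 3 infection with neutropenia means that some infections may still count.

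What is at stake is late follow-up of exposed subjects. Section 2.3.2 says the cause and clinical effects of the troponin increases are not known, so cardiac information collected months after dosing has some value. No text keeps subjects removed under this rule in LTFU.

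**Working it through.** **1. Is study exit needed in order to replace the subject?**

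Inputs: AMG 176 is planned on days 1, 8, 15 and 22 (Section 1.3, dosing footnote). The DLT period is at least 28 days, and 75% of planned AMG 176 doses are needed to be evaluable (Section 6.2.1.1).

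Doses needed: 0.75 × 4 = 3.

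| How delay is counted | Case | Limit passed | Doses received |
|---|---|---|---|
| From the planned day | Day-8 dose not given | after day 8 + 14 = 22 | 1 of 4 (25%) |
| From the planned day | Day-15 dose not given | after day 15 + 14 = 29, outside the 28 days | not applicable |
| From the last dose | Last dose on day 1 | after day 1 + 14 = 15 | 1 of 4 (25%) |
| From the last dose | Last dose on day 8 | after day 8 + 14 = 22 | 2 of 4 (50%) |

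The maximum is 50%, below 75% on either count. Without a DLT, such a subject is already non-evaluable and replaced under Section 6.2.1.1, with no need to leave the study. The result is limited to the 28-day window, because Section 6.2.1.1 allows the period to be extended for time-dependent events.

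**2. How much LTFU is at risk per subject?**

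Ceiling: 12 months / 3 months = 4 contacts, plus 1 echocardiogram at the first.

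The documents give no survival from EOT. The nearest figure is in Section 2.2.1: median overall survival of 4 to 6 months after HMA failure, which is the Part 1 population. Assume exponential survival with that median m, starting at EOT, so that S(t) = 2^(−t/m).

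| Month | m = 4 | m = 6 |
|---|---|---|
| 3 (echocardiogram) | 0.59 | 0.71 |
| 6 | 0.35 | 0.50 |
| 9 | 0.21 | 0.35 |
| 12 | 0.13 | 0.25 |
| Sum = expected contacts | 1.3 | 1.8 |

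The chance of reaching the echocardiogram visit is about 59% to 71%. Only 21% to 35% would reach a third contact, so most subjects would have no more than two.

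**3. What is protected elsewhere?**

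- EOT and safety follow-up examinations: every effort is asked for at premature treatment discontinuation (Section 1.3 footnotes).
- Acute cardiac work-up: telemetry, cardiologist evaluation and echocardiography at a hold (Section 6.2.2.1.3); imaging at EOT and for clinically significant cardiac events or biomarker rises (Section 8.4.5.1).
- Existing adverse events: followed to resolution or stabilisation (Section 8.4.6.3).
- Related serious events learned of later: still reportable (Section 8.4.6.1.3).
- Vital status: sought for all subjects (Section 8.4.4).

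This leaves the LTFU contacts on cardiac events, cardiac diagnostics and subsequent therapy, and the first-LTFU echocardiogram.

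**The case against.** The best defence is that a specific rule stands beside a general one. Section 7.1 is qualified by safety and feasibility, and a removal rule that the sponsor wrote can be filed under sponsor decision in Section 7.2.1. That supplies a label, but the removal remains automatic, which is what Section 7.1 advises against. Follow-up by phone or records is normally feasible.

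Several objections on reach do stand.

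- **Cause.** A reader might infer that every delay over 2 weeks ends participation. The closing sentence of Section 6.2.2.1.2 may send delays unrelated to AMG 176 to Medical Monitor review. Its scope is ambiguous, so automatic removal after an unrelated infection is not certain.
- **Dose decisions.** The sentence makes no exception for a subject with a DLT, so a reader might infer that DLTs drop out of escalation decisions. They do not: under Protocol Sections 6.2.1.1 and 9.3 and SAP Section 6.2, anyone with a DLT in the period stays DLT-evaluable, whether or not another subject is enrolled.
- **Troponin holds.** These are a possible route, not an established one. Table 6-2, footnote a, says: "Further treatment with AMG 176 may be considered for grade 1 elevations of troponin-I after a cardiology evaluation is completed". Section 4.3.1 reports no elevations at 120 and 180 mg/m² weekly, on a 3-of-4-week schedule.
- **Treatment-emergent window.** A reader might infer that removal also cuts short the SAP's 30-day adverse event window. That would require removal to set the subject's end-of-study date, whereas the Section 1.3 footnotes place it at LTFU completion or death.
- **Traceability.** SAP Section 9.2 plans no accountability summary, but the Section 9.6.8 listings give product dates, planned and actual doses and reasons for withholding. They would help find long delays, though they are not described as showing study exit or missed LTFU.

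**Conclusion.** The conflict is real, and its impact is minor. Section 6.2.2.1.2 requires study exit where Section 7.1 says not to remove subjects automatically and where Section 6.2.1.1 already provides replacement.

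Per affected subject, the exposure is at most 4 LTFU contacts and 1 echocardiogram. On average about 1.3 to 1.8 contacts would be reached, if survival is exponential from EOT with the median of 4 to 6 months that the protocol reports after HMA failure. That median is not measured from EOT, so these are indicative figures. The documents give no frequency for such delays, and none is assumed.

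A reader might infer a loss of response, event-free survival or overall survival results. The documents do not support that: vital status is collected separately, and the SAP reports early termination, no Part 2 enrolment and no formal efficacy analysis. What is at risk is late cardiac and subsequent-therapy information on a few exposed subjects.

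**What to change.** Replace the sentence in Section 6.2.2.1.2 with:

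> *The subject will be discontinued from AMG 176 (and, in Part 1B, from azacitidine unless the investigator and Medical Monitor agree to continue it), will remain on study for EOT, safety follow-up and LTFU per Section 7.1 unless consent is withdrawn, and will be replaced if not DLT-evaluable under Section 6.2.1.1.*

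Azacitidine has to be named because Section 8.1.3 ties the EOT visit to ending protocol-required therapies. The last clause also settles the case of a subject with a DLT.

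As the study closed early, the study report should state whether any subject left under this rule and, if so, which LTFU contacts or echocardiogram are missing. The SAP Section 9.6.8 listings are a starting point for finding them.

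The cost is one protocol sentence, which matters now mainly if the text is reused, and one statement in the report. All visits involved are already scheduled.
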